## Reactions to Research Participation Questionnaire (RRPQ)

Frequency of responses will be tabulated for 'reasons for participation' for the total sample and by PTSD+ participants and CSO participants. Descriptive statistics will be computed for total scores for subscales and reported for the total sample and by PTSD+ participants and CSO participants.

## 6. Safety Analyses

The primary measure of safety will be reports of adverse events. Adverse events are Treatment Emergent Adverse Events (TEAE) defined as those AE's that occurred after dosing and existing medical history diagnoses that worsened during the study. Verbatim terms on case report forms will be mapped to preferred terms and system organ classes using the MedDRA dictionary. For incidence reporting if a subject has more than one AE mapped to the same preferred term, that AE will be reported only once using the highest severity and closest relationship to study drug. Subject incidence of AEs will be displayed by group and by system organ class. AEs will also be summarized by severity. Subject incidence of SAEs will also be displayed. In addition to the listing of all AEs, a listing of SAEs and a listing of AEs leading to discontinuation of study drug will be included.

Summary tables of frequency listings of commonly reported AEs (Spontaneously Reported Reactions) mapped to preferred terms will be displayed during and after each experimental session by PTSD+ participants and CSO participants. Additional safety measures will be analyzed as follows:

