4.1 Planned Duration of Study and Visit Windows

The active part of the study will take about 2 months for the dyads to complete. There are additional remote follow-up visits, 3 months and 6 months after the primary assessment. Total study participation will last about 8 months.

Screening may take place over a 1-month period; final confirmation of enrollment may be combined with the first Preparatory Session. Additional time between the first and second Preparatory Session will be allowed if necessary for medication tapering. For example, the maximum washout would be seven weeks for participants tapering off of fluoxetine plus one week for stabilization. Enrolled dyads will immediately enter the Active Group (N=10). Dyads will participate in two Preparatory Sessions, two day-long Experimental Sessions with MDMA-facilitated CBCT sessions, and Integrative Sessions following each Experimental Session in conjunction with CBCT.

The Experimental Sessions will last 6 to 8 hours and will be scheduled 3 weeks apart, with an intervening course of non-drug therapy. The non-drug psychotherapy includes two Preparatory Sessions prior to the first Experimental Session and five Integrative Sessions after each Experimental Session. Integrative Sessions will be conducted by telemedicine (video conferencing whenever possible, telephone if there are occasions when video conferencing is not technically possible) and will include both members of the dyad. The sessions will follow a combination of the MDMA-assisted psychotherapy manual and the CBCT manual, with each method modified as needed to combine the therapies. Any delay between visits would result in a corresponding extension of study duration.

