5.2.2 Preparatory Psychotherapy Session (Visit 1 - Telemedicine Visit)

(Less than 4 weeks prior to Visit 2)

Participants who do not complete all screening activities will not be enrolled. Eligibility may be discussed by phone after screening is complete and at the time Visit 1 is scheduled but the final confirmation will occur at Visit 1. If all Inclusion Criteria and no Exclusion Criteria are met, eligibility will be confirmed with the participant.

- a. Complete a final review of Inclusion and Exclusion Criteria
- b. Assess General Wellbeing
- c. Confirm eligibility and willingness to participate in study
- d. Enroll participant and issue dyad number
- e. Ensure medical history and medication history is complete. After enrollment new events will be collected as AEs and new medications, as described in Sections 8.0 and 9.0.
- f. Discuss medication tapering, if applicable. Upon confirmation of eligibility, the PI or another designated study physician will consult the prescribing physician to initiate medication tapering for the PTSD+ participant and the CSO participant, if applicable, who must refrain from taking a psychiatric medication for the study. The prescribing physician's opinion about medication discontinuation will documented either in writing from the prescribing physician, or in writing by the study physician documenting phone contact with the prescribing physician. Tapering will follow a time course appropriate for the medication given its half-life, with the first Experimental Session scheduled to occur after complete washout. Individuals using opiates for pain management will be asked to decrease the dose or avoid taking their pain medication for 24 hours prior to Experimental Sessions if possible, as these medications may reduce the efficacy of MDMA. Participants will be permitted to take their prescribed opiate medication during this period if necessitated by pain flare-ups.

This first Preparatory Session will last 90 minutes and take place at Visit 1. During the Preparatory Sessions:

- a. This visit may be conducted by telemedicine or phone.
- b. Therapists may record all sessions to audio and video. The PTSD+ participant and the CSO participant will be given access to review audio or video recordings from the sessions upon request.

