8.5 Adverse Event Collection

The study physician will be responsible for reviewing and confirming all AEs and SAEs collected during the study. The therapists will collect AEs during study/telemedicine visits after enrollment.

All SAEs will be collected for the duration of the protocol. All SAEs which occur during the course of the trial, whether considered to be associated with the study drug or not, have to be reported within 24 hours of the Clinical Investigator's awareness of their occurrence. All SAE reports should be faxed to the sponsor. A fax number will be provided to the site in separate site-specific instruction for SAE reporting. In addition to the fax, the study physician, Clinical Investigator, or designee should call the CRA during normal working hours and verbally inform the CRA of the SAE. During off business hours or if medical advice is needed immediately please call the sponsor Medical Monitor. An SAE reporting instruction with all contact numbers will be provided to the site prior to study start.

Medical Monitor:

Page 69 of 89

[name]. [name] [name] [name] [contact]

Study Monitor contact information will be provided in a separate contact list.

Adverse events that will be collected for the duration of the protocol are:

- All SAEs will be collected through participant termination
- All AEs and spontaneously reported reactions will be collected on the day of drug administration and for seven days after each Experimental Session
- Any spontaneously reported reactions that have not resolved to the PTSD+ participant's or CSO participant's Baseline level of severity after seven days will be collected on the Adverse Event Report page until resolution
- Events requiring medical attention will be collected from enrollment through the PTSD+ participant's or CSO participant's last follow-up
- Events related to planned treatments or physician visits for Baseline conditions collected in the Medical History will not be collected unless there is an exacerbation of the condition
- Any Adverse Event leading to withdrawal from the protocol will be collected throughout the study
- All AEs related to changes in psychiatric status will be collected throughout the study

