## 3.4 Safety Objectives

The safety objectives of the study are to monitor and assure safety of all participants during and after the Experimental Sessions by assessing physiological effects, psychological distress, AEs, SAEs, medical events, spontaneously reported reactions, and suicidal ideation and behavior. All of the objectives below will be assessed in both participants.

- Suicidal ideation and behavior will be assessed with the Columbia Suicide Severity Rating Scale (C-SSRS) according to the Table 3: Time and Events.
- During Experimental Sessions, Subjective Units of Distress (SUD) and vital signs including blood pressure, heart rate, and temperature will be collected.
- Serious Adverse Events (SAEs) will be collected in both groups through Study Termination. All Adverse Events (AEs) will be collected on the day of drug administration through the Primary Endpoint and will be followed to resolution.
- Any spontaneously reported reactions will be collected from the day of the Experimental Session through seven days after both Experimental Sessions. Reactions that have not resolved to the participants' Baseline level of severity after seven days will be collected on the Adverse Event Report page until resolution.
- Assess General Wellbeing (clinician-rated) at all visits and phone calls for both the participants.
- AEs requiring medical attention will be collected through Study Termination.
- Events related to planned treatments or physician visits for Baseline conditions collected in the Medical History will not be collected unless there is an exacerbation of the condition.
- Any AE leading to withdrawal from the protocol will be collected throughout the study.
- All AEs related to changes in psychiatric status will be collected throughout the study.
- Baseline medications and changes to psychiatric medications will be collected throughout the study.
- Changes in pre-existing chronic pain and/or tinnitus symptoms will be collected

throughout the study using a Visual Analog Scale in any members of the dyad reporting these symptoms.

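### The SAP's treatment-emergent definition does not tie worsening of prior diagnoses to the first dose, so worsening during the pre-dose drug taper can enter the primary safety count

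*SAP*

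**What the plan says.** SAP 6. Safety Analyses states: "The primary measure of safety will be reports of adverse events". It then equates AEs with treatment-emergent AEs, defined as AEs arising after dosing together with "existing medical history diagnoses that worsened during the study". Only the first part of that definition mentions dosing. The second gives neither a start point nor a reference severity. The same paragraph says that a subject with several AEs under one preferred term is counted once, at the worst severity and strongest drug relationship recorded.

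Protocol 5.2.2 (Visit 1) confirms eligibility, enrols the dyad and closes the medical history: "After enrollment new events will be collected as AEs and new medications". Any psychiatric drug taper starts after eligibility is confirmed at that visit, "with the first Experimental Session scheduled to occur after complete washout". On the length of the taper, Protocol 4.1 says "the maximum washout would be seven weeks for participants tapering off of fluoxetine plus one week for stabilization".

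On when AE recording starts, the documents disagree. Protocol 5.2.2 and the row for all AEs in Table 3 start at Visit 1. SAP 3.4 says "All Adverse Events (AEs) will be collected on the day of drug administration through the Primary Endpoint". Protocol 8.5 says "All AEs and spontaneously reported reactions will be collected on the day of drug administration and for seven days after each Experimental Session". All of them collect AEs of psychiatric status throughout the study, and Table 3 ticks that row at Visits 1 and 2.

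**The concern.** In a single-arm study with no control group, timing relative to the first dose is one of the main ways to separate what follows MDMA with CBCT from what follows withdrawal of existing medication. The second part of the definition gives that up for prior diagnoses, where taper effects would be expected to show. A participant whose depression or anxiety worsens while coming off medication, before any MDMA, meets the SAP's wording for a treatment-emergent AE.

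The numbers are small, so one case is visible. With 10 people per role, one misplaced participant moves an incidence by 1/10 = 10 percentage points within that role, or 1/20 = 5 points overall. AE summaries are planned by role. If PTSD+ participants taper more often than their partners (an assumption; the documents do not say), the comparison between roles is affected as well.

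**Working it through.** The documents give no AE rate, expected count or pre-dose share, so there is no figure to reproduce. The check has three steps.

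**1. Can pre-dose worsening meet the definition?**
- Protocol 8.1 treats worsening of a pre-existing condition as an AE.
- Protocol 5.2.2 fixes the medical history at Visit 1, so a diagnosis held then is an existing one.
- The taper lies between Visit 1 and the first dose at Visit 3.
- Psychiatric-status AEs are recorded from Visit 1 in Table 3. SAP 3.4 and Protocol 8.5 also collect them throughout, despite starting all AEs on the dosing day.

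So psychiatric worsening during the taper is collected and meets the second part as written. Non-psychiatric worsening does so only if the earlier collection window applies.

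**2. What does the merging rule do?** Suppose that a prior condition worsens severely in the taper and is rated not related, because Protocol 8.1 requires that before exposure. It then worsens mildly after dosing and is rated probably related. Both map to one preferred term. Taking the worst severity and the strongest relationship gives one severe, probably related event. No such event occurred.

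**3. How much time is exposed?** Time from first dose to Visit 16:
- 3 weeks between sessions (21 days)
- 4 weeks to Visit 15 (28 days)
- 30 days to Visit 16

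21 + 28 + 30 = 79 days. To Visit 18, taking six months after Visit 15 as 182 days, it is 21 + 28 + 182 = 231 days.

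Pre-dose share = pre-dose days / (pre-dose + post-dose days):

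| Visit 1 to first dose | Share to Visit 16 | Share to Visit 18 |
|---|---|---|
| 1 day (short lead-in, no taper) | 1/80 = 1.3% | 1/232 = 0.4% |
| 31 days (about the one-month limit in Table 3) | 31/110 = 28% | 31/262 = 12% |
| 52 days (fluoxetine: 45 in Table 7 + 7) | 52/131 = 40% | 52/283 = 18% |
| 56 days (7 + 1 weeks, Protocol 4.1) | 56/135 = 41% | 56/287 = 20% |

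If worsening occurred at a constant rate, the count for a participant with a 56-day lead-in would be inflated 135/79 = 1.7-fold to Visit 16, or 287/231 = 1.2-fold to Visit 18. A higher rate during withdrawal would raise these figures. A participant who does not taper has no taper-related worsening, whatever the lead-in.

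**The case against.** Several points on the other side stand.

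- **New pre-dose events.** A reader might infer that the safety count is wrong in both directions, because new events before dosing are left out. The documents do not support that: leaving them out is what treatment-emergent means.
- **Disappearance.** Nor do those events vanish. SAP 6 adds a listing of all AEs, reports events needing medical attention from enrolment, and covers psychiatric-status AEs throughout. What they lack is a defined incidence table. The listing is also less clear than it could be, since the same paragraph equates AEs with treatment-emergent AEs.
- **Causality.** Treatment-emergent is a timing label. Relationship is judged separately, and Protocol 8.1 rates any event before exposure as not related. This is a real safeguard for the individual record, but it does not survive the merging rule in step 2.
- **Start of the window.** The SAP says during the study, not from enrolment. The Visit 1 start is inferred from Protocol 5.2.2 and Table 3, while SAP 3.4 and Protocol 8.5 start all AEs on the dosing day. Psychiatric-status AEs are collected early on either reading, so the core of the point remains.
- **Size.** The percentages are shares of calendar time, not of events. The documents do not say how many participants will taper. The 56-day figure is also at the edge of Protocol 5.2.1, which allows at most 8 weeks from the start of screening to the first session.
- **Weight.** This is a pilot of 10 dyads, not meant to lead to registration, with descriptive AE reporting. Estimating the harms of washout is not one of its objectives.

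**Conclusion.** The point holds as a defect in the definition. For prior diagnoses, the primary safety measure can include worsening that precedes any MDMA, and the merging rule can carry the severity of such an event onto a related post-dose one. This rests on reading the second part as written and on psychiatric-status AEs being collected from Visit 1. Elsewhere the SAP does separate washout from dosing: its C-SSRS baseline is Visit 2, after washout and before drug.

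The size of the error cannot be stated. The range of about 1% to 41% of time to Visit 16 shows how far the window can reach, and should not be read as a proportion of events misclassified.

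The wording leaves one narrower gap the other way. An AE that starts between Visit 1 and the first dose and worsens after dosing fits neither part, unless the worsening is recorded as a new event: its onset is before dosing and it is not medical history.

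**What to change.** 1. In SAP 6. Safety Analyses, define a treatment-emergent AE as an AE that starts, or a pre-existing condition or pre-dose AE that worsens in severity, at or after the first MDMA dose, up to a stated end date.
2. Apply the worst-severity and strongest-relationship rule only to events that meet that definition.
3. Add one table of AEs from enrolment to first dose, by role, labelled as pre-treatment events.
4. Reconcile the AE collection windows in Protocol 5.2.2, Protocol 8.5, SAP 3.4 and Table 3, so that the new table has one defined start.

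The cost is about two sentences in the SAP and one table built from event and dosing dates already recorded, plus an editorial reconciliation of the collection windows. No new data are needed where recording has followed Protocol 5.2.2 and Table 3. If a site has instead recorded all AEs only from the dosing day, the pre-treatment table would be limited to the categories collected throughout, and should say so.

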8.2 Spontaneously Reported Reactions

Commonly expected spontaneously reported reactions are collected on a separate CRF page and will be categorized as mild, moderate, or severe. Common, expected reactions are defined as those most frequently reported in the literature and include: Anxiety, Diarrhea, Difficulty Concentrating, Dizziness, Drowsiness, Dry Mouth, Fatigue, Headache, Heavy Legs, Impaired Gait/Balance, Impaired Judgment, Increased Irritability, Insomnia, Jaw Clenching or Tight Jaw, Lack of Appetite, Low Mood, Muscle Tension, Nausea, Need More Sleep, Nystagmus, Parasthesias, Perspiration, Restlessness, Rumination (increased private worries), Sensitivity to Cold, Thirst, and Weakness. Spontaneously reported reactions will be collected during the Experimental Session and the seven days of telephone contact following the Integrative Session that occurs on the day after each Experimental Session. Each reported reaction will be actively followed during follow-up phone calls or visits until resolution. Any reported event that is not listed as a Spontaneously Reported Reaction will be collected as an Adverse Event following the plan in Section 8.5 Adverse Event Collection. Any common reaction lasting longer than seven days will be tracked as an adverse event in order to obtain a resolution date.

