Qualitative safety analyses will examine adverse events, concomitant medications, and spontaneously reported reactions by summary tables listing maximum severity and

duration, as well as frequencies and percentages, tabulated overall and by PTSD+ participants and CSO participants. Quantitative safety analyses will examine vital signs, changes in Tinnitus and/or Pain, SUD, and C-SSRS, with comparisons made between by PTSD+ participants and CSO participants for effect of PTSD on safety measures.

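### For spontaneously reported reactions the SAP specifies only frequency listings, with no duration and no clear severity summary, although Protocol 12.0 calls for both

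*SAP*

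**What the plan says.** Protocol 12.0 (Data Analysis) describes the safety tables for adverse events, concomitant medications and reactions in one sentence. For reactions it names "spontaneously reported reactions by summary tables listing maximum severity and", and the same sentence goes on to add how long they lasted, with counts and percentages, for all participants together and for each role.

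Protocol 8.2 says that the expected reactions "are collected on a separate CRF page and will be categorized as mild, moderate, or severe". They are followed until they resolve. An event that is not on the reaction list is collected as an AE, and a listed reaction that lasts beyond seven days is then tracked as an AE so that a resolution date can be obtained.

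SAP section 6 (Safety Analyses) has two paragraphs that matter. The first is about AEs: a participant with repeat events under one preferred term is counted once ("that AE will be reported only once using the highest severity and closest relationship to study drug"), and "AEs will also be summarized by severity". The second is about reactions: "Summary tables of frequency listings of commonly reported AEs (Spontaneously Reported Reactions) mapped to preferred terms will be displayed". The only breakdown that it gives for that table is "during and after each experimental session by PTSD+ participants and CSO participants". SAP 6.0 adds that data not analysed under the plan stay out of tables and graphs and go into the listings.

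**The concern.** SAP 1.0 presents the SAP as based on the protocol's own analysis plan, yet its table for reactions is narrower than the protocol's and no reason is given. Assessing safety is a stated objective of the study, and these reactions are the expected acute effects of the drug.

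For common terms a frequency alone says little. Protocol 7.2 reports that in MP-1 anxiety, headache, fatigue, insomnia and lack of appetite were each reported by 40% to 80% of participants, in the placebo condition as well as the MDMA condition. Where a term is that common whatever the treatment, how severe it was and how long it lasted carry most of the information. Those are the two items that the SAP's reaction table does not name.

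**Working it through.** No power or sample-size figure is involved, so the check is a comparison of the texts, followed by simple counts.

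**Side by side**

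| Item for reactions | Protocol 12.0 | SAP reaction paragraph | SAP AE paragraph, if it applies |
|---|---|---|---|
| Frequency | yes | yes | yes |
| Percentage | yes | not named | not named |
| Maximum severity | yes | not named | yes |
| Duration | yes | not named | not named |
| By role | yes | yes | by group, not defined |
| Overall | yes | not named | not named |
| During/after each session | not named | yes | not named |

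Percentages are a minor matter, since SAP 6.0 describes nominal variables by frequencies and percentages in general. An overall column can be recovered by adding the two roles, provided that the counts are of participants. Severity and duration cannot be recovered in either way.

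**Does the AE paragraph cover reactions?** The SAP's own label for reactions makes them a kind of AE, and its AE definition (events after dosing) fits them. That supports yes. Protocol 8.2 keeps them on their own CRF page and sends only unlisted events to the AE form at onset, and the SAP gives reactions a paragraph of their own with its own table. That supports no, which is the more natural reading. The text does not settle it.

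**What is lost on each reading**

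- If the AE rules cover reactions: severity is summarized and participants are counted once per term, but duration is still missing.
- If they do not: severity and duration are both missing from the tables, and the counting unit for reactions is undefined.

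**Scale**

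- Protocol 8.2 lists 27 reaction terms.
- Participants: 10 dyads × 2 members = 20. Planned exposures: 20 × 2 sessions = 40.
- One severe reaction lasting six days and one mild reaction lasting an hour would each add 1/20 = 5% to their row. The during/after split might show that the first persisted, but not its severity.
- If 10 of 20 participants reported anxiety, the row would read 10/20 = 50% whether all ten were mild or all ten were severe, as long as they resolved within seven days.

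**Where the loss stops.** A reaction beyond seven days moves to AE tracking and so enters the AE severity summary. Its duration is still not tabulated, because the SAP names no duration for AEs.

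**The case against.** The best defence is that severity is not dropped at all. The SAP classes reactions as commonly reported AEs, so its highest-severity rule and its severity summary can be read to include them. That reading is open, and it means that no one can say flatly that the SAP omits severity. It does nothing for duration.

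Other limits also stand:

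- A reader might infer that a severe, lasting reaction counts the same as a mild, brief one throughout the report. The documents do not support that, because reactions beyond seven days become AEs with a severity summary.
- A reader might infer that severity goes unreported. It would still be in the listings, which can be read through for 20 participants. What is lost is the summary.
- A reader might infer that a reaction noted on several days will be counted several times. That follows only if the once-per-term rule is taken to exclude reactions.
- The MP-1 range of 40% to 80% applied to both conditions, so it shows that the terms are common, not that MDMA caused them.
- Protocol 12.0 is loosely drafted. Its single list also covers concomitant medications, to which maximum severity cannot apply. Severity and duration for reactions are still the evident intent.
- The documents do not show that the reaction CRF page records a resolution date. That longer reactions move to AE tracking in order to obtain one suggests that it may not.

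Finally, this is an uncontrolled study of ten dyads that is not meant to lead to registration, so little turns on one table. That limits the weight of the point, but it gives no reason for the SAP to do less than the protocol states.

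**Conclusion.** The two documents specify different tables for the same data, and the SAP's is the weaker. Duration of reactions is summarized nowhere. Severity of reactions is ambiguous: missing on the more natural reading and present on the other. The gap applies to 27 terms over 40 planned exposures and bites on reactions that resolve within seven days.

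This rests on reading the Protocol 12.0 list as applying to reactions, and on SAP 6.0 sending data not analysed under the plan to listings only. The primary analysis and the conduct of the study are not affected. It is a reporting gap in a stated safety objective, and it should be closed before the SAP is final.

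**What to change.** In SAP section 6, replace the frequency listings with a table that follows Protocol 12.0:

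- for each reaction term and session, the number and percent of participants at each maximum severity, overall and for PTSD+ and CSO participants, keeping the during/after split if wanted;
- each participant counted once per term at the highest severity, with a statement that this rule applies to reactions;
- duration summarized in days, as far as the daily contacts in the week after each session (Protocol 5.2.5) and the resolution data allow;
- a statement of whether reactions also enter the AE severity table, and how a reaction carried over to AE tracking is shown in each.

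The cost is SAP wording and one table shell. Severity is already graded on the reaction CRF page. The drawback is that duration may be only coarse if that page holds no resolution date; the SAP should then state how days are derived.
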